21.2 PRIMARY ENDPOINT

The primary endpoints are the rate of bothersome visual symptoms and the rate of reported difficulty with an activity due to visual symptoms at 6 months postoperative.

The first primary endpoint is the rate of bothersome visual symptoms,

. The second primary endpoint is the rate of reported difficulty with an activity due to one or more visual symptoms, determined by a "Yes" response to the question "Is there anything you have a lot of difficulty with, or do not do, because of [visual symptom]") at 6 months postoperative.

The frequency and proportion of subjects with bothersome visual symptoms for one or more visual symptoms, and the frequency and proportion of subjects reporting difficulty with an activity due to one or more visual symptoms will be reported along with the two-sided, 95% confidence interval at the 6-month visit.

Justification of Effect Size:

Using an assumed value of 20% for bothersome visual symptoms or difficulty with an activity due to visual symptoms, and a sample size of 240 evaluable subjects per group, a two-sided 95% confidence interval will estimate the observed rate of bothersome visual symptoms to within 4.2 percentage points.

21.3 ADDITIONAL ENDPOINTS

The frequency and proportion of subjects with each response will be reported for the individual visual symptom items for overall and with and without correction.

The frequency and proportion achieving each acuity level will be reported for monocular visual acuity.

[figure not shown]
Descriptive statistics will be reported for mean percent reduction in cylinder, refractive cylinder, cylinder vs preoperatively-predicted cylinder, spherical equivalent and spherical equivalent vs preoperatively-predicted spherical equivalent. The frequency and proportion of eyes within 0.50 D and within 1.00 D of the preoperatively-predicted values will be reported for refractive cylinder and spherical equivalent. Percent reduction in cylinder will be calculated for each eye using the following formula:

100*((Postop Ref. Cyl. - Preop K. Cyl.)/(Target Ref. Cyl. - Preop K. Cyl.)) Key: Ref. Cyl.=absolute refractive cylinder; K. Cyl.=keratometric cylinder;

[figure not shown]
Refractive data will be referred to the corneal plane prior to determining percent reduction in cylinder.

Enrollment data, demographic data, subject accountability data and operative complications/procedures will be reported using descriptive statistics. Visual symptom findings, adverse events and other key data will be reported at 1 year for subjects who experienced a repositioning procedure during the study or who were reported with bothersome visual symptoms at the 6-month visit.

The frequency and proportion of primary and fellow eyes with medical/lens findings will also be reported. In addition, rates of IOL repositioning procedures (secondary surgical intervention) due to IOL misalignment, rates of explants related to visual symptoms, rates of refractive procedures performed during the study period, and other adverse events will be reported.

21.4 INTERIM REPORTS

21.5 SAMPLE SIZE CALCULATIONS

With a sample size of 240 subjects and assuming a 20% rate of bothersome visual symptoms or difficulty with an activity due to visual symptoms, a two-sided 95% confidence interval will estimate the observed rate of bothersome visual symptoms to within 4.2 percentage points.

[figure not shown]
To achieve 240 higher-cylinder group subjects and 240 lower-cylinder group subjects evaluable at 6 months, assuming an initial 20% screen-fail rate and a 5% lost-to-follow-up rate, up to 634 total subjects will be enrolled.

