## 4 POSTOPERATIVE ANALYSES – PRIMARY ENDPOINTS

There are two primary endpoints for this study, rate of bothersome visual symptoms and rate of difficulty with an activity due to the symptoms at 6-month postoperative.

The first primary endpoint is the rate of bothersome visual symptoms,

The second primary endpoint is the rate of reported difficulty with an activity due to one or more visual symptoms, determined by a

"Yes" response to the question "Is there anything you have a lot of difficulty with, or do not do, because of [visual symptom]") at 6 months postoperative.

The frequency and proportion of subjects with bothersome visual symptoms and the frequency and proportion of subjects reporting difficulty with an activity due to one or more visual symptoms will be reported along with the two-sided, 95% confidence interval at the 6-month visit.

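### With 240 subjects per group and a 20% rate, the two-sided 95% confidence interval is about ±5.1 points, not the ±4.2 stated in Protocol 21.2, Protocol 21.5 and SAP 7

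*Protocol*

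**What the plan says.** Protocol 21.5 opens "With a sample size of 240 subjects and assuming a 20% rate of bothersome visual symptoms" (or of difficulty with an activity) and concludes that "a two-sided 95% confidence interval will estimate the observed rate of bothersome visual symptoms to within 4.2 percentage points". SAP 7 repeats this. Protocol 21.2, under Justification of Effect Size, makes the same claim, beginning "Using an assumed value of 20% for bothersome visual symptoms or difficulty with an activity due to visual symptoms", and settles that the number applies to each group: "a sample size of 240 evaluable subjects per group".

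The level matches the planned reporting. SAP 4 says that the two primary-endpoint proportions "will be reported along with the two-sided, 95% confidence interval at the 6-month visit", and Protocol 21.2 says the same. No interval method is named in the readable text of either document.

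Protocol 21.5 then works back from the evaluable target in each group to the number enrolled: "assuming an initial 20% screen-fail rate and a 5% lost-to-follow-up rate, up to 634 total subjects will be enrolled".

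**The concern.** The precision statement is a closed calculation. Sample size, rate, confidence level and sidedness are all given, so the half-width follows from them, and it does not come to 4.2 points.

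This matters because the readable text offers no other reason for 240 per group: no power statement, no hypothesis test and no margin. Precision is what the sample size is said to buy, and it is overstated. If the 20% assumption holds, the final report will almost certainly show wider intervals than the plan promised, for either primary endpoint. It is also unclear whether 4.2 points was a target that 240 fails to meet, or only a description of what 240 gives. Those two readings lead to very different sample sizes.

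**Working it through.** **Inputs.** n = 240 evaluable per group (Protocol 21.2); p = 0.20 (Protocol 21.2, 21.5; SAP 7); two-sided 95%, z = 1.960 (same sections; reporting level in SAP 4); stated half-width 4.2 points.

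**Attempt to reproduce 4.2.**

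- Standard error = √(p(1 − p)/n) = √(0.16/240) = 0.02582, or 2.582 points.
- Half-width = 1.960 × 2.582 = **5.06 points** (interval 14.9% to 25.1%).
- Ratio to the stated figure: 5.06/4.2 = 1.20.

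**Other interval methods, two-sided 95%, 48 of 240 events.**

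| Method | Below 20% (points) | Above 20% (points) | Mean half-width (points) |
|---|---|---|---|
| Normal approximation (Wald) | 5.06 | 5.06 | 5.06 |
| Wilson | 4.57 | 5.52 | 5.04 |
| Jeffreys | 4.68 | 5.40 | 5.04 |
| Agresti-Coull | 4.59 | 5.54 | 5.06 |
| Exact (Clopper-Pearson) | 4.87 | 5.63 | 5.25 |

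The shortest arm of any of them is 4.57. A continuity-corrected Wald interval gives 5.27.

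**Other sample sizes, Wald 95%.** n = 253 (implanted per group) gives 4.93, n = 480 (both groups pooled) gives 3.58, and n = 506 gives 3.49. The 95% half-width for the difference between groups is 7.16. None is 4.2.

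**What does give 4.2.** With z = 1.645 the Wald half-width is 1.645 × 2.582 = 4.25 points (4.247 before rounding, so 4.2 to one decimal). That multiplier belongs to a two-sided 90% interval or a one-sided 95% bound. Its use here is an inference: no readable text shows the formula or mentions either interval. Put the other way, ±4.2 points at these inputs has confidence 2Φ(4.2/2.582) − 1 = 89.6%.

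**Dependence on the rate (Wald 95%, n = 240).** 10%: 3.8 points; 15%: 4.5; 20%: 5.1; 25%: 5.5; 30%: 5.8. The half-width is 4.2 or less only if at most 30 of 240 subjects (12.5%) report the endpoint: 30 events give 4.18 and 31 give 4.24. If the true rate is 20%, 30 or fewer events has a binomial probability of about 0.15%. These counts are for Wald intervals.

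**Sample size that would deliver 4.2 at 20%.** n = 0.16 × (1.95996/0.042)² = 348.4, so 349 evaluable per group.

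- Implanted at 5% loss: 349/0.95 = 367.4, so 368 per group, 736 in total.
- Enrolled at 20% screen failure: 368/0.80 = 460 per group, 920 in total.

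If 4.2 is read as anything that rounds to it (up to 4.25 points), n = 0.16 × (1.95996/0.0425)² = 340.3, so 341 per group. Then 341/0.95 gives 359 and 359/0.80 gives 449 per group, 898 in total.

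**Check of the plan's own enrolment chain.** 240/0.95 = 252.6, so 253 per group and 506 in total. 253/0.80 = 316.25, so 317 per group and 634 in total. Both figures reproduce, so the error is confined to the precision figure.

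**The case against.** The best case on the other side accepts the arithmetic and disputes how much it matters. The readable analysis consists of frequencies, proportions and confidence intervals. The intervals will be computed from the data, no readable decision rule uses 4.2, and the evaluable targets are approximate. If the sponsor is content with 240 per group, no subject, endpoint or analysis changes. All of this stands, and it limits the consequence to the stated rationale for the sample size. It does not make the statement true.

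Part of the text is also withheld. A figure is missing after the precision statement in Protocol 21.5, the study-design justification in Protocol 4 is blank, and the SAP's table appendix refers to inferential comparisons that its readable text does not describe. Another use of 4.2, or another justification for 240, could be there. The remark that nothing else depends on 4.2 therefore holds for the readable text only. The disputed statement itself is complete in all three places, and hidden text cannot change the half-width at the stated inputs.

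Two technical points also stand. First, a bound of 5.1 points is exact only for the symmetric normal-approximation interval; the upper arms of the Wilson, Jeffreys, Agresti-Coull and exact intervals are longer, so corrected wording should name the method. Second, 349 per group takes 4.2 as exactly 4.200; allowing for rounding, the range is 341 to 349 per group, or 898 to 920 enrolled.

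**Conclusion.** The stated precision is wrong. At 240 per group and a 20% rate the two-sided 95% half-width is 5.06 points by the normal approximation, and 5.04 to 5.27 as a mean half-width across the methods tried, against 4.2 stated. Precision is overstated by about 0.9 point in each group.

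The figure is what is out of line, not the confidence level, because both documents commit to two-sided 95% intervals for the primary endpoints. The conclusion rests only on the plan's own inputs. It does not depend on the inference that 1.645 was used in place of 1.960. The error should be corrected because it is the only readable justification for the sample size and it appears in both documents; the planned analysis and the enrolment arithmetic are unaffected.

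**What to change.** In Protocol 21.2, Protocol 21.5 and SAP 7, replace 4.2 percentage points with about 5.1 percentage points (normal approximation). Keep 240 per group and the two-sided 95% level. If exact intervals are intended, state about 5.6 points (the longer arm) and name the method. In either case the named method should be the one used to report the primary endpoints.

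The sponsor should confirm in writing that about 5.1 points is acceptable. If so, the cost is three wording edits and a slightly less favourable precision claim, with enrolment unchanged at up to 634.

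If 4.2 points at two-sided 95% was the requirement, rewording is not enough. About 349 evaluable subjects per group would be needed, meaning 736 implanted and about 920 enrolled at the plan's own loss and screen-failure rates, against 506 and 634 now.

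Relabelling 4.2 as a 90% figure is a weaker repair, because the sample-size text would then no longer match the 95% intervals to be reported.

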APPENDIX D - SLIT-LAMP EXAM RATINGS

CELLS				
Grade	Cells in Field (Field is a 1x1 mm slit beam)			
0	<1			
0.5+	1 - 5			
1+	6 - 15			
2+	16 - 25			
3+	26 - 50			
4+	>50			

CELLS

FLARE			
Grade	Description		
0	None		
1+	Faint		
2+	Moderate (iris and lens details clear)		
3+	Marked (iris and lens details hazy)		
4+	Intense (fibrin or plastic aqueous)		

B. Ratings of Corneal Edema

Corneal edema should be classified according to the haziness of the epithelium, the number of microcysts observed, and the clouding of the stroma.

Amount	Grade	Description		
None	0	Normal transparency: a. No epithelial or sub-epithelial haziness b. No microcysts c. No stromal cloudiness		
Trace	+1	 a. Barely discernible localized epithelial or sub-epithelial haziness, and/or b. 1 to 20 microcysts, and/or c. Barely discernible localized stromal cloudiness 		
Mild	+2	 a. Faint but definite localized or generalized epithelial, sub-epithelial or stromal haziness/cloudiness, and/or b. 21-50 microcysts 		
Moderate	+3	 a. Significant localized or generalized epithelial, sub-epithelial or stromal haziness/cloudiness and/or b. 51-100 microcysts 		
Severe	+4	 a. Definite widespread epithelial or stromal cloudiness, giving dull glass appearance to cornea or numerous coalescent bullae (please note the number and location of bullae), and/or b. >100 microcysts or bullae, and/or c. Numerous striae (please note the number and location of striae or folds) 		

JOHNSON & JOHNSON SURGICAL VISION, INC. C. Posterior Capsule Striae Grading Scale

The following five-point grading scale is to be used for rating striae in the posterior capsule:

Amount	Grade	Description	
None	0	None	
Trace	+1	One detectable, barely noticeable striae	
Mild	+2	One or two prominent striae	
Moderate	+3	Three or more prominent striae, but visibility of retina is not impacted	
Severe	+4	Three or more prominent striae affecting visualization of retina	

D. Posterior Capsule Opacification Grading Scale

Below is the five-point grading scale to be used for PCO determination:

Amount	Grade	Description		
None	0	Normal posterior capsule with no area of opacity. Red reflex bright.		
Trace	+1	Some loss of transparency involving the posterior capsule. Red reflex fairly bright		
Mild	+2	Aild loss of transparency with cloudiness extending through nost of the posterior capsule. There may be a few Elschnig's bearls in the posterior capsule. Red reflex mildly diminished.		
Moderate	+3	Moderate loss of transparency with difficulty visualizing the retina. There may be multiple Elschnig's pearls in the posterior capsule. Red reflex markedly diminished.		
Severe	+4	Posterior capsule very opaque with inability to view the retina. The posterior capsule may have confluent Elschnig's pearls and fibrous scarring. Red reflex barely visible.		

E. IOL Glistenings

Use the following scale to grade IOL glistenings, using a slit beam 2.0 mm wide and 10.0 mm long:

Amount	Grade	Description
None	0	No glistenings visible
Rare	+0.5	<10 glistenings visible
Trace	+1	10-19 glistenings visible
Mild	+2	20-29 glistenings visible
Moderate	+3	30-39 glistenings visible
Severe	+4	≥ 40 glistenings visible

## SAP CHANGE HISTORY

Version	Section(s)	Page(s)	Description of Change(s)	Rationale for Change(s)
1.0	N/A	N/A	Original	N/A

## 1 INTRODUCTION

This document summarizes the statistical methods to be implemented for this post approval study of the Tecnis Symfony® Toric lenses, Models ZXT300, ZXT375 with ZXT150 as the control lens. This study is a 6-month, prospective, multicenter, bilateral, non-randomized open label comparative clinical trial conducted at up to 50 sites. Subjects will be bilaterally implanted with a TECNIS Symfony IOL, either toric (Models ZXT150, ZXT225, ZXT300 or ZXT375) or non-toric (TECNIS Symfony Extended Range of Vision IOL, Model ZXR00). Each eye may have a different TECNIS Symfony IOL implanted, as determined by the surgeon and the TECNIS Symfony Toric IOL calculator; however, at least one eye must be implanted with either a Symfony Toric IOL Model ZXT150 (lower-cylinder group) or a Model ZXT300 or ZXT375 (higher-cylinder group) and the fellow eye must have the same or a lower toric power. The eye with the highest toric power IOL will determine the model group.

The purpose of this post-approval study is to evaluate the rates of bothersome visual symptoms for the higher-cylinder Symfony Toric IOLs, Models ZXT300 and ZXT375, compared to the lower-cylinder Symfony Toric IOL, Model ZXT150. The first primary endpoint is the rate of bothersome visual symptoms

Symptom Questionnaire (PRVSQ). The second primary endpoint will be the rate of those having a lot of difficulty as measured in the PRVSQ.

Other endpoints are individual visual symptom ratings included in the PRVSQ, rates of IOL repositioning procedures (secondary surgical intervention) due to IOL misalignment, rates of explants due to visual symptoms, distance visual acuities, mean percent reduction in absolute cylinder, mean refractive cylinder, mean refractive cylinder compared to the preoperatively-predicted cylinder, mean spherical equivalent, spherical equivalent compared to the preoperatively-predicted spherical equivalent, percent of eyes with cylinder and spherical equivalent (MRSE) within 0.50 D and within 1.00 D of the preoperatively-predicted spherical equivalent, rates of medical and/or lens findings, and rates of other adverse events.

The key time point for reporting will be at 6 months. however, any subject that undergoes a lens repositioning procedure due to IOL misalignment, or reports "bother that impacts daily living

at 6 months, will be followed through 1 year

postoperatively.

## 2 ANALYSIS POPULATIONS

## 2.1 ANALYSIS POPULATIONS/HANDLING OF MISSING DATA

The higher cylinder group will consist of subjects with a ZXT300 or ZXT375 in at least one eye. To be included in the lower cylinder group a subject must have a ZXT150 in at least one eye and not have a ZXT300 or ZXT375 in the other eye. For the primary endpoints and other questionnaire data, the primary analysis population will be all bilaterally-implanted subjects having available data at the 6-month visit, with data reported separately for the higher- and lower-cylinder groups. For the final report,

For other questionnaire items, bilaterally-implanted subjects with available data at six months postoperative will be used for analysis. Refraction, monocular visual acuity, medical/lens findings and adverse event data will be reported for primary eyes (higher cylinder eye or first eye implanted if same IOL model in both eyes) and fellow eyes. Data will be reported separately for the higher-cylinder group and the lower cylinder control group.

For monocular endpoints, data will be presented by primary and fellow eyes. Primary eye of a subject is defined as the eye having a higher toric power. If both eyes have the same Toric lens model, the first eye undergoes surgery will be defined as the primary eye and the second eye will be defined as the fellow eye.

Descriptive statistics will typically include sample size (N), mean, standard deviation (SD), median, minimum (Min.), and maximum (Max.) as appropriate for continuous variables. For categorical data, the frequency and proportion will be computed.

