7. STUDY PRODUCTS

7.1 INTRAOCULAR LENSES

TECNIS Symfony IOLs, both toric and non-toric, are posterior-chamber, 1-piece, aspheric, hydrophobic acrylic foldable IOLs and are to be implanted in the capsular bag following cataract extraction. The Symfony IOLs have a spherical posterior optic with a diffractive surface to provide an extended depth of focus and an anterior aspheric optic; the Symfony Toric IOLs also have a toric surface to correct for ocular astigmatism.

The TECNIS Symfony Toric Model Series ZXT IOLs included in this study are intended for cataract patients with pre-existing corneal astigmatism that, when taking surgically-induced astigmatism into account and using the TECNIS Symfony Toric Calculator's PCA algorithm, have approximately 2.00 D to 3.00 D (higher-cylinder group) or 0.75 D - 1.50 D (lower-cylinder group) of predicted corneal astigmatism to be corrected (**Table 1**).

ZXT IOL	Cylinder Power (D)		Correction Range Based on	
Model	IOL Plane	Corneal Plane	Combined Corneal Astigmatism (Preoperative Kcyl ^a + SIA ^b)	
ZXT150	1.50	1.03	0.75 – 1.50 D	
ZXT225	2.25	1.55	1.50 – 2.00 D	
ZXT300	3.00	2.06	2.00 – 2.50 D	
ZXT375	3.75	2.57	2.50 – 3.00 D	

TABLE 1 Symfony Toric IOL Astigmatism Correction Range

^a Keratometric cylinder

^b Surgically-induced astigmatism

[°] Model ZXT225 eyes may be included in the study; however, the fellow eye must require either a ZXT300 or ZXT375 IOL. Model ZXT225 is not the subject of this study.

The Model ZXT IOLs have two sets of four axis orientation marks 180° apart in the outer periphery of the anterior optic surface (**Figure 1**) to indicate the meridian of the lowest power (flat meridian). These axis orientation marks are for proper alignment of the flat meridian of the IOL with the steep meridian of the corneal curvature.

[figure not shown]

FIGURE 1: Drawing and Photograph of a Model Series ZXT IOL

INDICATION

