The TECNIS Symfony Toric Extended Range of Vision IOLs, including Models ZXT150, ZXT225, ZXT300, and ZXT375, are indicated for primary implantation for the visual correction of aphakia and for reduction of residual refractive astigmatism in adult patients with greater than or equal to 1 diopter of preoperative corneal astigmatism, in whom a cataractous lens has been removed. The lens mitigates the effects of presbyopia by providing an extended depth of focus. Compared to an aspheric monofocal IOL, the lens provides improved intermediate and near visual acuity, while maintaining comparable distance visual acuity. The Model Series ZXT IOLs are intended for capsular bag placement only. Note that Model ZXT225 may be included in the study; however, the fellow eye must require either a Model ZXT300 or ZXT375 IOL. Model ZXT225 is not the subject of this study.

The TECNIS Symfony Extended Range of Vision IOL, Model ZXR00, is indicated for primary implantation for the visual correction of aphakia in adult patients with less than 1 diopter of pre-existing corneal astigmatism, in whom a cataractous lens has been removed. The lens mitigates the effects of presbyopia by providing an extended depth of focus. Compared to an aspheric monofocal IOL, the lens provides improved intermediate and near visual acuity while maintaining comparable distance visual acuity. The Model ZXR00 IOL is intended for capsular bag placement only. Note that Model ZXR00 will only be implanted in fellow eyes for this study.

STORAGE AND DISTRIBUTION

All lenses will be obtained from the site's own inventory. All study lenses should be stored in the original packaging and kept in a dry place. Lenses should not be stored in direct sunlight or at temperatures greater than 45° C (113°F). Each lens is packaged in a lens tray and sealed in a peel-pouch. The lens is sterile as long as the package has not been opened or damaged and the shelf-life expiration date has not been exceeded.

Table 2 lists the general design characteristics of the Symfony Toric IOLs:

CHARACTERISTICS	Symfony Toric IOL Model Series ZXT
Lens Design	1-piece foldable posterior-chamber lenses with a toric-aspheric anterior surface, a diffractive design on the posterior surface, and a maximum and a minimum radii of curvature perpendicular to each other
Lens Model	Surface-treated SENSAR [®] soft acrylic (hydrophobic acrylic with a covalently-bound UV absorber)
DIMENSIONAL FEATU	RES
Overall Diameter	13.0 mm

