11.9 PROTOCOL DEVIATIONS

Any departure from the protocol procedures represents a protocol deviation. Protocol deviations may be subject-based (e.g., inclusion/exclusion criteria, informed consent deviation, etc.) or procedural-based (e.g., out-of-interval visits, non-compliance with testing procedures, etc.). All protocol deviations will be documented using protocol deviation case report forms.

Any deviation made to protect the life or physical well-being of a subject in an emergency, as well as any use of a study device without obtaining informed consent, must be reported to JJSV within 5 working days. Protocol deviations will be monitored by JJSV, and if the non-compliance is persistent or egregious, JJSV may take action, including but not limited to termination of the investigator's participation in the study. The investigator is also responsible for informing the reviewing IRB of instances of protocol non-compliance in accordance with the IRB requirements.

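### Does leaving ZXT225 out of the SAP's lower-cylinder rule put wrong subjects into the control group?

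*SAP*

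**What the plan says.** SAP 2.1 puts anyone with a ZXT300 or ZXT375 in either eye into the higher-cylinder group. For the lower-cylinder group it says that "a subject must have a ZXT150 in at least one eye and not have a ZXT300 or ZXT375 in the other eye". The primary population follows: "the primary analysis population will be all bilaterally-implanted subjects having available data at the 6-month visit". For single-eye tables, "Primary eye of a subject is defined as the eye having a higher toric power".

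SAP 1 states the principle behind the groups: "The eye with the highest toric power IOL will determine the model group", and "the fellow eye must have the same or a lower toric power". The Protocol synopsis, section 4 and section 8.1 say the same.

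The Table 1 note in Protocol 7.1 deals with the intermediate lens: "Model ZXT225 eyes may be included in the study; however, the fellow eye must require either a ZXT300 or ZXT375 IOL". It adds that "Model ZXT225 is not the subject of this study". Table 1 gives the order of cylinder power at the IOL plane: ZXT150 1.50 D, ZXT225 2.25 D, ZXT300 3.00 D, ZXT375 3.75 D. ZXR00 is non-toric.

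On deviations, Protocol 8 does not let the investigator waive eligibility criteria, and Protocol 11.9 says: "All protocol deviations will be documented using protocol deviation case report forms".

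**The concern.** The SAP 2.1 sentence is the one a programmer would code, and it excludes only two of the three lenses stronger than ZXT150. Coded literally, it makes a ZXT150/ZXT225 subject a control. Under SAP 1 the ZXT225 eye is the stronger one, and ZXT225 defines neither group.

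Nothing in the readable text removes such a subject afterwards. The primary population is everyone implanted in both eyes with 6-month data, and deviations are only documented. The subject would therefore count in the control rate for both primary endpoints. Because the primary eye is the stronger one, the ZXT225 eye would also appear in the control group's primary-eye tables for refraction, acuity, findings and adverse events.

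At stake is a control group that contains a lens outside the study question, with membership depending on which sentence the programmer follows. A related worry is that both groups may contain subjects with a weaker or non-toric lens in the fellow eye, while the primary endpoints are counted per subject.

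**Working it through.** **Step 1: classify every lens pair.** Five models give 5 × 6 / 2 = 15 unordered pairs. Each pair is sorted by the literal SAP 2.1 rule and by the SAP 1 strongest-lens rule, then checked against the eligibility rules.

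| Pairs | Number | SAP 2.1 | SAP 1 | Eligible? |
|---|---|---|---|---|
| ZXT300 or ZXT375 in at least one eye, any model in the other | 9 | higher | higher | yes |
| ZXT150 with ZXT150 or ZXR00 | 2 | lower | lower | yes |
| ZXT150 with ZXT225 | 1 | lower | neither | no |
| ZXT225 with ZXT225 or ZXR00 | 2 | neither | neither | no |
| ZXR00 with ZXR00 | 1 | neither | neither | no |

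The total is 9 + 2 + 1 + 2 + 1 = 15. The two rules agree on 14 pairs, including all 9 + 2 = 11 eligible ones. The exception, ZXT150/ZXT225, breaks two rules. A ZXT225 fellow eye is stronger than the qualifying ZXT150 eye, and ZXT225 is present without a ZXT300 or ZXT375 beside it.

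**Step 2: what one misplaced subject does.** Inputs are the 20% assumed rate and 240 evaluable subjects per group (SAP 7, Protocol 21.5). Suppose k of the 240 are misplaced and have event rate q, while the rest have 20%. The control rate then shifts by

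k × (q − 0.20) / 240.

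- k = 1, event present: 0.80 / 240 = +0.33 percentage points.
- k = 1, event absent: −0.20 / 240 = −0.08 points.

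**Step 3: several subjects.** The documents give no count. With k = 5, which is purely an assumption:

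- q = 0: 5 × (−0.20) / 240 = −0.42 points.
- q = 0.30: 5 × 0.10 / 240 = +0.21 points.
- q = 1: 5 × 0.80 / 240 = +1.67 points.

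**Step 4: compare with sampling error.** The 95% half-width at 20% and n = 240 is 1.96 × √(0.20 × 0.80 / 240) = 5.06 points. The plan prints 4.2, which this formula gives with a multiplier of 1.645 (1.645 × √(0.16 / 240) = 4.2). That is a separate matter, and the comparison here holds against either figure. A shift as large as 5.06 points would need 0.0506 × 240 / 0.80 ≈ 15 such deviations, every one with the event.

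**The case for a change.** The strongest reply is that an analysis-population section exists partly to say what happens to deviations, so pointing to ineligibility does not close the gap. The deviation is also conceivable. Second eyes are operated on up to about a month after the first, at up to 50 sites drawing on their own lens stock. ZXT150 and ZXT225 are adjacent models whose correction ranges meet at 1.50 D. The synopsis lists ZXT225 among the fellow-eye lenses without repeating the Protocol 7.1 condition. A few words in SAP 2.1 would bring all 15 pairs into line.

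Part of this stands: the sentence is looser than it should be, and the readable text does not say where the pair goes. Three things limit it.

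- The synopsis also carries the rule that the fellow eye may not exceed the qualifying eye, so it does not admit the pair either.
- Such a subject would be visible. The calculator choice for each eye is kept as source (Protocol 11.3), the implanted model is on the operative form (11.5), deviations go on their own form (11.9), and SAP 3.1 plans a frequency table by IOL.
- Excluding ZXT225 by name would drop an implanted, followed subject from both groups because of a deviation. That is not clearly better than keeping the subject in a stated group and flagging it.

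The public copy of SAP 2.1 also breaks off in mid-sentence straight after the primary population is defined, so handling of this case cannot be ruled out.

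Mixed lens pairs are allowed by design, and the SAP 2.1 wording does not bear on them. A table of the endpoints by pairing would be an optional extra. It would be imprecise: at a 20% rate the half-width is 1.96 × √(0.16 / 120) = 7.2 points with 120 subjects and 1.96 × √(0.16 / 60) = 10.1 with 60. The documents give no size or direction for any effect of pairing.

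**Conclusion.** The mismatch in wording is real, but it does not touch the planned analysis. Every eligible subject falls in the same group whether the programmer follows SAP 2.1 or SAP 1. The two part company only for one disallowed pair, where each occurrence would shift the control rate by between −0.08 and +0.33 percentage points, well inside the sampling error of about 5.1.

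This rests on the plan's 20% rate and 240 controls, and on such deviations being few. The documents imply the last point through eligibility rules that may not be waived, but give no count. If the pair did occur, the recorded lens models would reveal it, and a statistician reviewing deviations before the final analysis would decide on its placement and say so in the report. This is a gap in deviation handling that analysts fill sensibly, and amending the plan would not alter the result of a trial run as written.
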